10.5.1.2. Secondary Efficacy Endpoints

Comparing each CBP-201 regimen to placebo:

- IGA (0-1): Proportion of subjects with both IGA score 0 to 1 (clear; almost clear) and a reduction of ≥ 2 points at Week 16
- EASI:
 - EASI-50: Proportion of subjects achieving $\geq 50\%$ reduction of EASI score from baseline at Week 16
 - EASI-75: Proportion of subjects achieving $\geq 75\%$ reduction of EASI score from baseline at Week 16
 - EASI-90: Proportion of subjects achieving $\geq 90\%$ reduction of EASI score from baseline at Week 16
- Change from Baseline to W16 in weekly average PP-NRS
- Number of AD flares from baseline through Week 16
- Number of days with AD flare through Week 16

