13.2. Sample Size Justification

The first primary efficacy endpoint is percentage of reduction of EASI at week 16. While the final analysis is planned to be analysis of variance (SAS[®] PROC MIXED for ANOVA) with confounding covariates, for simplicity, the sample size is calculated using a simpler 2-sample independent t-test. Based on the preliminary results at week 4 and more empirical data, the following input parameters were used for power and sample size calculation:

Parameters:

- Type I error (α) = 0.05 (two-sided)
- The non-inferiority margin of 35% between the CBP-201 300 mg Q2W vs. Placebo
- Common standard deviation (σ) = 45%
- Effective sample size: 44 per arm, after considering of 20% dropout rate from 55 randomized per arm

Hypotheses:

$$H_0: \Delta_{\text{CBP-201-300 mg Q2W} - \text{Placebo}} = 0$$

$$H_1: \Delta_{\text{CBP-201-300 mg Q2W} - \text{Placebo}} \neq 0$$

Statistical test: Two-sample t-test for mean difference

Based on method described above, a sample size of 220 (55 per arm, or effective sample size of 44 per arm considering 20% dropout rate) will provide 95% power to detect the treatment effect on the primary endpoint between the CBP-201 300 mg Q2W vs. Placebo.

To further detect the other treatment effects vs. Placebo, and also preserve the alpha at 0.05 level, a hierarchical multiple testing procedure is adopted, from the highest dose (300 mg Q2W) to the lowest dose (150 mg dose Q2W), until statistical significance at 0.05 level is not achieved.

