13.6.2. Analysis for secondary efficacy endpoint

The secondary efficacy endpoints are as follows:

- IGA (0-1): Proportion of subjects with both IGA score 0 to 1 and a reduction of ≥ 2 points at Week 16
- EASI:
 - EASI-50: Proportion of subjects achieving $\geq 50\%$ reduction of EASI score from Baseline at W16
 - EASI-75: Proportion of subjects achieving $\geq 75\%$ reduction of EASI from Baseline at W16
 - EASI-90: Proportion of subjects achieving $\geq 90\%$ reduction of EASI from Baseline to W16
- Change from baseline to Week 16 in weekly average of PP-NRS
- Number of AD flares from Baseline through W16
- Number of days with AD flare from Baseline through W16

For categorical secondary efficacy endpoints, counts, percentage, and confidence interval obtained based on the Clopper-Pearson method will be presented for each CBP-201 regimen and placebo, respectively. For quantitative secondary efficacy endpoints, the method for statistical analysis is similar to those for primary efficacy endpoints.

Proportion of subjects achieving IGA (0-1), and proportion of subjects achieving EASI-50, EASI-75, or EASI-90 in the EASI score will be plotted by treatment and scheduled time. Mean change (\pm SD) from baseline for P-NRS will be plotted by treatment and scheduled time.

For the secondary efficacy endpoints, summary statistics will be provided by treatment group. The clopper-pearson confidence interval will also be provided for endpoints of proportions. No formal statistical comparison will be performed.

In this study, subjects are permitted to take TCS treatment (rescue) for AD flares. It is expected subjects randomized to placebo arm will require TCS medication more often or for longer periods.

All other details for efficacy analyses will be handled as discussed in the Study's SAP.

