- Proportion of subjects achieving ≥ 4 -point reduction in weekly average of PP-NRS from Baseline to Week 16 and Week 20.
- Change in Patient Oriented Eczema Measure (POEM) from Baseline to Week 16 and Week 20.
- Change in percentage body surface area (BSA) of AD involvement from Baseline to Week 16 and Week 20.
- Change in Severity scoring of AD (SCORAD) from Baseline to Week 16 and Week 20.
- Change in Dermatology Life Quality Index (DLQI) from Baseline to Week 16 and Week 20.
- Number of subjects with AD flares from Baseline to Week 8 and from Week 8 to Week 16 and Week 20.
- Number of AD flares (defined as escalation of therapy evidenced by Topical corticosteroids (TCS) usage) from baseline through Week 16.
- Number of days with AD flare through Week 16.

D. Safety Endpoints

- Adverse events (AEs) reported
- Vital Signs (VS)
- Physical examinations

- Injection site changes
- Safety laboratory parameters
- Electrocardiogram (ECG) parameters
- Number (%) of subjects displaying positive anti-drug antibodies (ADA)

4. Study Design

A. Design Overview

This is a phase 2, randomized, double-blind, placebo-controlled study to assess the efficacy, safety, PD and PK profile of CBP-201 administered to eligible adult subjects with moderate to severe AD. The study period includes a treatment period of 16 weeks and a follow-up period of 8 weeks.

Approximately 220 subjects who meet eligibility criteria and consent to participate in the study are randomly assigned in a 1:1:1:1 ratio to one of the following treatment groups:

- CBP-201 1800 mg (150 mg Q2W): CBP-201 600 mg (4 vials) on D1, 1 vial of CBP-201 and 1 vial of placebo on W2 and the same dose Q2W thereafter through W16. Total CBP-201 dose over 16 weeks: 1800 mg.
- CBP-201 3000 mg (300 mg Q2W): CBP-201 600 mg (4 vials) on D1, CBP-201 300 mg (2 vials) on W2 and Q2W thereafter through W16. Total CBP-201 dose over 16 weeks: 3000 mg.
- CBP-201 1800 mg (300 mg Q4W): CBP-201 600 mg (4 vials) on D1, placebo (2 vials) on W2, CBP-201 300 mg (2 vials) on W4, W8, W12 and W16, alternating with placebo (2 vials) on W6, 10, and 14. Total CBP-201 dose over 16 weeks: 1800 mg.
- Placebo: 4 vials on D1, 2 vials on W2 and Q2W thereafter through W16.

B. Study Population

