Study subjects are adults between 18 and 75 years old (both included) at the screening visit (Screening) with AD (according to American Academy of Dermatology Consensus Criteria, Eichenfield 2014) present for at least 1 year prior to the baseline visit (Baseline). In terms of AD, subjects must have an inadequate response to AD treatment with a topical regimen of corticosteroids, phosphodiesterase inhibitors or calcineurin inhibitors, or for whom topical treatments are otherwise medically inadvisable, and have IGA score ≥ 3 , EASI score ≥ 16 , and BSA for total AD involvement $\geq 10\%$ at Screening and Baseline.

C. Sample Size Determination

A sample size of 220 (55 per arm, providing approximately 44 completers per treatment group assuming 20% dropout rate) will provide 95% power to detect at treatment effect on the primary endpoint of percentage reduction of EASI at week 16 between the CBP-201 300 mg Q2W vs. Placebo. This power calculation

is based on the use of a two-sided two-sample t test at the $\alpha=0.05$ level of significance. Based on the preliminary results at Week 4 and empirical data, the mean between-group difference is assumed to be equal to 35 percentage points and the pooled standard deviation is assumed to be 45% using 2-sample independent t-test.

D. Treatment Randomization

Patients will be randomized at a 1:1:1:1 ratio into the following 4 groups: CBP-201 1800 mg (600mg load D1 then 150 mg Q2W), CBP-201 3000 mg dose (600mg load D1 then 300 mg Q2W), CBP-201 1800 mg dose (600mg load D1 then 300 mg Q4W), or placebo, respectively. The randomization is not stratified.

E. Assessment Schedule

The date at which the subject is randomized will be referred to as the “Baseline/Day 1” visit. Subjects will be requested to attend the scheduled visits for the Treatment Period every 2 weeks from their Baseline/Day 1 visit through Week 16. The acceptable visit window for scheduled visits during the Treatment Period is ± 2 days. After Week 16 of treatment, subjects will no longer receive any treatments but will return for an additional 8 weeks for follow-up visits. The acceptable visit window for scheduled visits during the Follow-up Period is ± 3 days.

In the case of an early termination (ET) from the study for any reason, study completion assessments should be performed as detailed for the study completion visit and should be completed within 7 days of the ET, whenever possible.

F. Clinical Trial Material

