 - defined as the total number of AD flares with an onset date from baseline to Week 16. Number of AD flares will be summarized using descriptive statistics for each treatment group using OC. Number and percentage (along with the 95% CI) of subjects with at least one AD flare during each period will be provided for each treatment group.
- Number of subjects with AD flares from Baseline to Week 8 and from Week 8 to Week 16 and Week 20:
 - AD flares on Baseline to Week 8 and from Week 8 to Week 16 will be defined similarly by AE onset date as described above. AD flares that start before Week 8 and are ongoing or resolve after Week 8 will be counted in the first period (baseline to Week 8) only.
- Number of days with AD flares through Week 16:
 - the duration of each AD flare is defined as (resolution date of AE – onset date of AE + 1) among subjects with at least one AD flare. For subjects reporting more than one flare, the total subject-days of duration would be calculated and used in statistical summary. Details regarding calculation of duration of AE are described in section 9 below. Number of days with flares will be summarized using descriptive statistics for each treatment group.

All efficacy endpoints will be summarized for FAS using descriptive statistics or frequency counts and percentage for all scheduled visits, for each treatment group.

9. Safety Analyses

Safety analyses will use data from the Safety population. Safety data will be summarized using frequency tables (counts with percentages) and will be presented by treatment and scheduled visits if applicable. Continuous safety data will be summarized using descriptive statistics by treatment and scheduled visits. Data will be compared to the reference ranges provided and be checked for abnormality and/or clinically relevant changes from baseline, where applicable. No formal statistical comparisons will be performed for safety endpoints.

A. Exposure

The following exposure parameters will be defined and summarized by treatment group using descriptive statistics:

- Number and percentage of subjects receiving any injection of study drug at each visit
- Number of injections received at each visit and overall
- Volume (mL) of study drug injected at each visit and overall
- Dose (mg) of study drug injected at each visit and overall
- Number and percent of subjects that have dose interruptions, as well as those with dose interruptions due to AEs

B. Adverse Events

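### Two protocol secondary flare endpoints become 'other' endpoints in the SAP without being declared, and are summarised without regard to time observed

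*SAP*

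**What the plan says.** **Tier.** Protocol 10.5.1.2 lists "Number of AD flares from baseline through Week 16", and the days with flare over the same period, as secondary endpoints. Protocol 13.6.2 repeats this, and the synopsis calls them key secondary. SAP 3.B (secondary endpoints) contains neither. SAP 3.C (other endpoints) contains both, including "Number of days with AD flare through Week 16".

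**Declared changes.** SAP Section 11 lists three: added Week 20 timepoints, a new testing order, and LOCF in place of WOCF for the main analysis. None concerns flares.

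**Method in the protocol.** Section 13.6.2 says: "For quantitative secondary efficacy endpoints, the method for statistical analysis is similar to those for primary efficacy endpoints". The same section then says that secondary endpoints receive summary statistics and no formal comparison.

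**Method in the SAP.** Section 8.D counts flares with onset between baseline and Week 16 and continues: "Number of AD flares will be summarized using descriptive statistics for each treatment group using OC". It adds the number and percentage of subjects with at least one flare, with a 95% CI. Flare-days are the summed AE durations among subjects who had a flare. Section 5.J leaves the flare endpoints as observed cases without imputation. No rate, person-time denominator or rule for subjects who leave before Week 16 is given.

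**The concern.** Section 11 is where a reader looks for departures from the protocol. Two listed secondary endpoints changed tier, and that reader would not learn of it. POEM, BSA, SCORAD and DLQI, which the protocol always classed as other endpoints, keep a primary-type model in SAP 8.D. The flare endpoints do not.

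The summary also has a structural weakness. A count accrues over time. A subject observed for four weeks can contribute only four weeks of flares, but the definition does not distinguish that subject from one observed for sixteen. If follow-up differs between arms, the difference in totals mixes flare rate with time observed. The gap is plainest for the Week 8 to Week 16 period: a subject who left at Week 4 has no observed time in it, and the SAP does not say whether that subject enters the denominator.

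Flare-days have a second problem. Having flared is a post-randomisation outcome, so the subjects summarised in each arm are selected by something treatment may affect. Protocol 13.6.2 itself expects more frequent or longer topical steroid use on placebo, so this comparison carries clinical information.

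**Working it through.** **The plan's own figure.** The documents give no planning figure for flares. The only stated calculation is for EASI: "Type I error (α) = 0.05 (two-sided"), "the mean between-group difference is assumed to be equal to 35 percentage points", "Common standard deviation (σ) = 45"%, and 55 × 0.80 = 44 effective subjects per arm, which "will provide 95% power to detect the treatment effect". It reproduces: 95.4% by the normal approximation and 95.0% by the noncentral t. It does not bear on flares; only its 20% dropout rate is used below.

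**Set-up.** Let q be the share of an arm leaving the study before Week 16, and f the mean fraction of the 16 weeks lost per leaver. With a constant flare rate and exit unrelated to flares, the raw total captures 1 − q·f of the expected 16-week count. The apparent active/placebo ratio is

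true ratio × (1 − q_active·f) / (1 − q_placebo·f).

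Two assumed exit patterns are used: uniform over 16 weeks (f = 0.50), and all at Week 4 (f = 12/16 = 0.75).

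**At the documented 20% dropout, equal in all arms**

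- Uniform exit: 1 − 0.20 × 0.50 = 0.90, so 10% of flares are uncounted.
- All at Week 4: 1 − 0.20 × 0.75 = 0.85, so 15% are uncounted.
- The factor is the same in both arms and cancels. The ratio is unbiased.

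**At unequal dropout (assumed; the documents give no split by arm)**

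| Placebo / active dropout | Exit | Factor | True 1.00 appears as | True 0.50 appears as |
|---|---|---|---|---|
| 30% / 10% | uniform | 0.95/0.85 | 1.12 | 0.56 |
| 30% / 10% | Week 4 | 0.925/0.775 | 1.19 | 0.60 |
| 10% / 30% | uniform | 0.85/0.95 | 0.89 | 0.45 |
| 10% / 30% | Week 4 | 0.775/0.925 | 0.84 | 0.42 |

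**Is a leaver recorded as flare-free?** Not necessarily, because onsets before exit are counted. At an assumed 1 flare per 16 weeks (Poisson), the chance of no recorded flare is exp(−1) = 37% for a completer, 1 − exp(−1) = 63% for a uniform-time leaver, and exp(−0.25) = 78% for a Week 4 leaver. At an assumed 0.5 flares per 16 weeks the figures are 61%, 79% and 88%.

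**Flare-days.** Let p be the share of an arm that flares and m the mean flare-days among those who do. The mean over all subjects is p·m; the SAP summarises m. If treatment lowers p and leaves m alone, this summary shows no difference. SAP 9.B calculates no duration when an end date is wholly missing, so a flare still open at exit can drop out of the total. Section 8.D gives no rule for cutting durations at Week 16.

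**The case against.** The case for leaving the plan alone has several parts that stand.

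- **No test is lost.** A reader might infer that the SAP removed a planned formal comparison. It did not. Protocol 13.5.5 confines formal comparison to the primary endpoint, and 13.6.2 rules it out for secondary endpoints. The sentence there about a method like the primary's sits beside a descriptive-only statement, so descriptive reporting fits one reading of the protocol.
- **The protocol had no time adjustment either.** The primary-type ANOVA has no offset, so the SAP did not introduce this weakness.
- **Early leavers do not simply look flare-free.** That stronger reading contradicts SAP 8.D, which keeps every onset before exit. Nor does the SAP say that a short count is treated as a full one; it is silent on whether leavers are kept at their observed total or excluded.
- **Exposure is limited.** Protocol 7.1.2.3 and 11.1.4 keep subjects under observation after treatment stops, so only study withdrawal shortens the flare window. Discontinuations by arm, the percentage with any flare, and AE listings with dates will all be available. Differential follow-up would be visible, though not adjusted for.
- **The unequal splits are assumptions.** The direction of any bias is unknown.

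A mismatch in protocol version is an unlikely explanation. The SAP cites Amendment 3.0, and both the testing order and the WOCF rule that Section 11 says it replaces match the supplied protocol.

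These points narrow the concern. They do not answer the undeclared move, the missing rule for early leavers, or the conditioning of flare-days on having flared.

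**Conclusion.** The point holds in limited form. The undeclared reclassification and the absence of any time denominator can be read directly from the documents. The cost is tier, disclosure and an interpretable between-arm estimate; no error rate is affected.

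The numerical effect is modest. At the planned dropout, equal across arms with the same exit timing, about 10% to 15% of flares are missed in each arm and the ratio is unaffected. A 20-point imbalance in study withdrawal would shift the ratio by roughly 11% to 19%, against the drug if placebo subjects leave more and in its favour if active subjects do. These figures assume a constant flare rate, exit unrelated to flares, and dropout splits and timing that the documents do not supply. They do not support a claim that the planned comparison is biased in a known direction.

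**What to change.** 1. Restore both flare endpoints to SAP 3.B, or add the reclassification and its reason to Section 11.
2. State how subjects who leave before Week 16 enter the count and the percentage with at least one flare, including the Week 8 to Week 16 period.
3. Report flares per person-time to Week 16 by arm. Add a rate ratio against placebo with 95% CI from a negative binomial model with log(days observed) as offset, labelled exploratory.
4. Report flare-days as a proportion of days observed in all FAS subjects, counting zero for those without a flare and cutting durations at Week 16 or study exit, whichever comes first.

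The onset, resolution and exit dates are already collected, so the cost is SAP wording and slight extra programming. The offset corrects for unequal follow-up. It does not correct for exit that is itself related to flare risk, and the report should say so.

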150 mg group, by 52.8% in the 300 mg group versus 22.8% in the placebo group. P-NRS response rates (>3-point decrease) were greater for the 150 mg (50%, 4/8) and 300 mg groups (57%, 4/7) versus the placebo group (25%, 2/8) on Day 29.

Safety: CBP-201 appeared to be safe and well-tolerated when administered to male and female adult patients with moderate to severe AD, at SC doses of 75 mg, 150 mg, and 300 mg. These conclusions were based on the following findings from 23 patients in the pooled CBP-201 group who received at least one dose of CBP-201 and 8 of 8 patients in the placebo group.

- There were no SAEs, life-threatening TEAEs, or deaths reported on study.
- There were no TEAEs leading to the discontinuation from the study.
- The majority of TEAEs were mild. The number and severity of TEAEs and treatment related TEAEs did not increase with increasing CBP-201 dose level. Of 51 TEAEs reported across the pooled CBP-201 group, 9 events were deemed by the Investigator to be related to study drug, and 3 of 11 TEAEs in the placebo group were deemed related to placebo treatment. There was no treatment related severe TEAEs reported.
- The most common Adverse Events (AE) during the study were exacerbation of AD (26.1% in the combined CBP-201 group and 37.5% in placebo group), headache, and upper respiratory tract infection.
- By dose across the CBP-201 treatment groups, there were no apparent differences between the different dosing groups in terms of study treatment related TEAEs.
- There were no clinically significant injection site reactions that were reported as AEs
- There were no clinically significant and/or study drug-related changes in vital signs, ECG parameters, or physical examination findings.
- Immunogenicity assay results showed 5 of 23 patients (21.7%) had a treatment-induced positive response for ADA with very low titration. Overall, the immunogenicity of CBP 201 varied inversely with the CBP-201 dose, with the incidence of treatment-induced ADA positive response observed to decrease with greater CBP 201 doses.

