7.1.2.3. AD Flares and Rescue Treatment

AD is a chronic relapsing skin condition that is characterized by periods of disease flare or escalation of symptoms. Many flare definitions rely on a physician's assessment or subject report (38), however a relatively recent review suggests that an escalation of treatment (or rescue) and days of topical corticosteroid (TCS) use were good indicators of flare and flare duration (39). Therefore, when an AD flare occurs, its onset and duration will be documented as an AE by the location(s) of flare involvement. If the Investigator determines that the flare is severe enough to merit "rescue" treatment, document the choice of TCS and

instructions for its use and the duration of such permitted rescue TCS treatment. The subject need not be discontinued in this situation. Permitted TCS medications to treat AD flares may include the following:

- Cream based preparations or lotion in hair bearing areas
- Low to moderate potency TCS (WHO classification VII-IV) equivalent to class VII – IV according to the U.S classification are allowed. The TCS regimen will be adjusted to the flare activity and tolerability by the subject, and stopped when lesions are cleared.
 - Examples:
 - Methylprednisolone acetate 0.1%
 - Mometasone furoate 0.1%
 - Betamethasone valerate cream 0.1%
- If possible, Investigators should attempt to limit the first step of rescue therapy to permitted TCS rescue treatment and escalate to systemic medications only for patients who do not respond adequately after the treatment of permitted TCS.

If a patient receives any other rescue treatment including other topical rescue treatments (apart from permitted TCS and bland emollients), systemic corticosteroids or nonsteroidal systemic immunosuppressive/immunomodulating drugs (cyclosporine, methotrexate, mycophenolate mofetil, azathioprine, Janus kinase inhibitors, biologic agents, etc), the study treatment will be immediately discontinued. In this situation, subjects should remain in the study and continue with study procedures (complete the schedule of study visits and assessments) but will not receive additional study drug administration.

Investigators should make every attempt to conduct efficacy and safety assessments (eg, disease severity scores, safety labs) immediately before administering any rescue treatment. An unscheduled visit may be used for this purpose if necessary.

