11.1.4. General Guidelines for AE Reporting

Collection of AEs and SAEs will commence from the time the subject signs the informed consent to participate in the study and continue until the end of the study. All AEs must be entered on the corresponding pages of the CRF, regardless of causality or severity. AEs include new AEs, worsening baseline conditions, clinically significant laboratory findings, disease-related signs and symptoms that were not present at baseline, and any events or findings that the Investigator feels are clinically significant.

Information collected concerning AEs will include the following:

- Name of the event (whenever possible, diagnosis or single syndrome should be reported instead of symptoms)
- Start date
- Stop date
- Severity (i.e., mild, moderate, severe, potentially life-threatening, death)

- Relationship to study treatment (related, not related)
- Action taken with the study treatment (dose not changed, drug interrupted, drug withdrawn, not applicable, unknown)
- Outcome (recovered/resolved, recovering/resolving, not recovered/not resolved, resolved with sequelae, fatal, unknown)
- Seriousness of event (SAE or non-SAE)

Pretreatment AEs are defined as any untoward medical occurrence in a clinical investigation subject who has signed informed consent to participate in a study but prior to administration of any study medication; it does not necessarily have to have a causal relationship with study participation. Treatment-emergent adverse events (TEAEs) are defined as AEs that developed or worsened during the treatment-emergent period. The treatment-emergent period is from first administration of study treatment to end of the follow-up period. Pre-existing conditions (present at the time of signing of informed consent) are considered concurrent medical conditions and should not be recorded as AEs unless they worsen in severity or increase in frequency. Screening evaluation findings (e.g., laboratory tests, ECG, etc.) should not be recorded as Pretreatment AEs unless related to study procedures.

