All AEs will be coded using MedDRA version 24.0 or higher. A treatment-emergent AE (TEAE) is defined as any AE that occurs or worsens after initiation of study treatment.

The duration in days of each AE will be calculated as (resolution date of AE – onset date of AE + 1). For the determination of TEAEs and calculation of durations for AD flares, the following rules regarding partial dates will be applied:

- If only the day is missing for a start date, the 1st of the month will be imputed. If the new estimated date falls before the date of first dose, while the known month and year match the month and year of the first dose, the date of first dose will be used as the new estimated date. The AE will be considered as a TEAE.
- If only the day is missing for an end date, the last day of the month will be imputed. If the new estimated date falls after the date of last study visit, the date of last study visit will be used as the new estimated date.
- If both the day and the month are missing for a start date or end date, no imputation will be used, and the duration will not be calculated. However, if the year of start is the same or greater than the year of the first dose date, the AE will be considered as treatment emergent.

- If the start date or end date is completely missing, duration will not be calculated. However, an event with completely missing start date will be considered as treatment emergent.

An overall summary of AEs will be presented by treatment and overall. The summary will include the total number of events, frequency counts and percentages with:

- All AEs
- TEAEs
- Treatment-emergent Serious Adverse Events (SAEs)
- Treatment-related TEAEs
- Treatment-related treatment-emergent SAEs
- TEAEs leading to study drug discontinuation
- Injection site reactions
- AEs of Special Interest (AESIs): conjunctivitis, keratitis and other ophthalmic events evaluated by an ophthalmologist.

Summaries of the incidence of TEAEs will be displayed by treatment according to the following:

- All TEAEs by SOC in descending order of frequency (in the sequence of all subjects, all active treatments, CBP-201 3000 mg [300 mg Q2W] group) and PT in the same order of frequency
- All TEAEs by SOC, PT, and maximum severity (1 mild, 2 moderate, 3 severe, 4 life-threatening, 5 death)
- All TEAEs by SOC, PT, and maximum causality (not related, related) to study treatment
- All serious TEAEs by SOC and PT
- All AESI by SOC and PT

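### The SAP's flare-days variable leaves out subjects without a flare, has no Week 16 cut-off and gives open flares no duration, so it does not measure flare days through Week 16

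*SAP*

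**What the plan says.** Protocol 10.5.1.2 and 13.6.2 list the number of AD flares and the number of days with flare through Week 16 as secondary endpoints, and the synopsis calls them key secondary. SAP 3.C lists both under other efficacy endpoints. SAP 11, which records changes from the protocol, does not mention the move.

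SAP 8.D takes flares from the AE record. The duration of each is the resolution date minus "onset date of AE + 1) among subjects with at least one AD flare". If a subject has more than one flare, "the total subject-days of duration would be calculated and used in statistical summary". The same section closes with a general statement: "All efficacy endpoints will be summarized for FAS using descriptive statistics or frequency counts".

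On period boundaries, SAP 8.D ties the number of flares to an onset date up to Week 16. For the number of subjects with flares it has a rule at Week 8: "AD flares that start before Week 8 and are ongoing or resolve after Week 8 will be counted in the first period". It has no such rule at Week 16 for days.

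SAP 9.B supplies the date rules for flare durations. An end date missing only its day is set to the end of the month and capped at the last study visit. With day and month both missing, there is no duration. Finally: "If the start date or end date is completely missing, duration will not be calculated".

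Protocol 11.1.4 lists the AE outcomes to be collected: "Outcome (recovered/resolved, recovering/resolving, not recovered/not resolved, resolved with sequelae, fatal, unknown". Protocol 7.1.2.3 says of a flare that "its onset and duration will be documented as an AE by the location(s) of flare involvement".

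**The concern.** The endpoint is meant to compare flare burden between each regimen and placebo over the treatment period. As derived, it departs from that in three ways.

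- **Who is counted.** Having a flare is a post-randomization outcome. If flare-free subjects carry no value, each arm's summary is conditioned on that outcome, and a treatment that prevents flares gets no credit for it here. Protocol 13.6.2 expects placebo subjects to need topical steroid more often or for longer. The derivation drops the first of these.
- **Which days are counted.** With no cut at Week 16, days in the 8-week follow-up after the last dose are added to a variable named for the treatment period.
- **Which flares are counted.** A flare that has not resolved has no resolution date and so no duration. The longest flares are the most likely to be lost.

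The last two act in opposite directions, and the documents give nothing from which to judge the net effect. The reported flare days could show no difference, or favour placebo, when flare days per randomized subject favour CBP-201.

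**Working it through.** The documents give no expected value for flare days, so there is no planned figure to reproduce. The check applies the SAP rule to defined cases.

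**1. Is there a zero, a cut-off or a closing date anywhere?**

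- *Zero for flare-free subjects:* none in SAP 8.D. The sentence on the full analysis set names the population but gives no value. SAP 5.J leaves endpoints that it does not list as observed cases without imputation.
- *Cut at Week 16:* none for days. The only cap, in 9.B, is the last study visit, and it applies only to an end date whose day is missing.
- *Closing date for an open flare:* none. Under 9.B a completely missing end date means no duration.

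**2. Single flares.** Week 16 is D113 and the end of study is D169. SAP days = resolution − onset + 1. Days through Week 16 = min(resolution, 113) − onset + 1, with an open flare counted to D113.

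| Onset | Resolution | SAP days | Days through Week 16 |
|---|---|---|---|
| D106 | D169 | 169 − 106 + 1 = 64 | 113 − 106 + 1 = 8 |
| D29 | D169 | 169 − 29 + 1 = 141 | 113 − 29 + 1 = 85 |
| D85 | none | no value | 113 − 85 + 1 = 29 |
| D50 | D60 | 11 | 11 |

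The rule is right only for a flare that resolves by Week 16. In the second row it gives more days than the 113 in the window.

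**3. Arm level.** The only flare-like rates in the documents are from study CBP-201AU002 (Protocol 5.4.2): "exacerbation of AD (26.1% in the combined CBP-201 group and 37.5% in placebo group". With 8 placebo and 23 CBP-201 patients these are 3/8 = 0.375 and 6/23 = 0.2609. Days per flaring subject are assumed. The all-subject mean is rate × days, and differences are placebo minus active.

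| Assumed days, placebo / active | SAP difference | All-subject means | All-subject difference |
|---|---|---|---|
| 7 / 7 | 0 | 2.63 / 1.83 | 0.80 |
| 14 / 14 | 0 | 5.25 / 3.65 | 1.60 |
| 28 / 28 | 0 | 10.50 / 7.30 | 3.20 |
| 14 / 18 | −4 (favours placebo) | 5.25 / 4.70 | 0.55 (favours active) |
| 14 / 12 | 2 | 5.25 / 3.13 | 2.12 |

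With 14 placebo days, the all-subject means are equal when active days reach 5.25 / 0.2609 = 20.1. Between 14 and 20.1 active days the two summaries point in opposite directions.

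**4. Subjects behind the mean.** At 55 per arm the SAP mean would rest on about 55 × 0.375 = 20.6 placebo and 55 × 0.2609 = 14.3 active subjects.

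**The case against.** The best defence is that these are gaps in wording rather than wrong instructions. The restriction to subjects with a flare sits in the sentence that defines the duration of a flare, and a duration exists only where there is a flare. The summary sentence that follows carries no restriction, the full analysis set is named in the next paragraph, and the endpoint's title says Week 16. A careful programmer might supply zeros and a cut. That is possible, but the SAP states neither, and a programmer who follows the text would do neither.

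On open flares, the AE outcome list is generic, the rules in 9.B are introduced as rules for partial dates, and completers have 8 more weeks in which a flare can resolve. This limits how often the gap would matter, but it supplies no rule for when it does.

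The numerical illustration is weak as evidence on flare rates. The two rates come from 8 and 23 patients given four weekly doses, with exact 95% intervals of 9% to 76% and 10% to 48% (Fisher p = 0.66). The active figure pools all dose levels, and every duration is assumed. The reversal needs longer flares on active than on placebo. If flares are shorter on active, as in the 14 / 12 row, both summaries agree in direction. All of this stands. It limits what can be said about size, not whether the derivation matches the endpoint.

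It is also true that nothing is formally tested on flare days, and that the SAP reports the percentage of subjects with at least one flare and lists every AE with its dates. A reader could roughly restore the zeros from that percentage. The Week 16 cut and the open flares would need a new derivation from the listing.

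**Conclusion.** The concern holds. Applied as written, SAP 8.D and 9.B give a total flare duration among subjects who flared. The total is not limited to the treatment period and omits flares without a resolution date. This is not the protocol's secondary endpoint.

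The size depends on assumed durations. With the CBP-201AU002 rates and equal durations of 7 to 28 days, the SAP summary shows no difference while the all-subject difference is 0.8 to 3.2 days. The direction can reverse if flares on active last moderately longer. The net bias from the missing cut-off and the open flares is unknown.

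The harm is confined to the flare-days result. The primary analysis and the gatekeeping sequence are untouched, and flare prevention would still show in the percentage of subjects with a flare. The SAP should be changed, but the trial's main conclusion does not depend on it.

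One further point is conditional. If flares at several locations are entered as separate AEs, which the protocol wording allows but does not require, summed durations count the same day more than once.

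**What to change.** Redefine the variable in SAP 8.D. For every subject in the full analysis set, count the distinct calendar days from D1 to the Week 16 visit, or last contact if earlier, on which at least one flare AE is ongoing. Score 0 if there is none. Close any flare still open at that date, and state what is done with a flare recorded as resolved whose end date is completely missing. Counting distinct days also removes any double counting across locations. Report by arm, and add flare days per days observed to allow for early withdrawal. Duration among subjects who flared can stay as an extra descriptive line.

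Two smaller items belong in the same edit. State whether the definition by topical steroid use, which SAP 3.C attaches to the number of flares, also applies to flare days; flare days without steroid use should not be dropped by default. Record in SAP 11 that both flare endpoints moved from secondary to other.

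The cost is minor SAP wording and programming, since Protocol 11.1.4 already requires start date, stop date and outcome for every AE. The drawback is a variable with many zeros: the median may be 0, and the mean should be read beside the percentage who flared.
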